The proposed study will evaluate the safety, tolerability, and pharmacokinetics (PK) of multiple ascending doses (MAD) of SLV213 in healthy male and female participants, 18-65 years of age. This study will help to select the most likely suitable dose (e.g., at Maximum Tolerated Dose [MTD]) for the treatment of patients with COVID-19 in a pivotal study. This double blind, placebo-controlled study will consist of three sequential cohorts of 12 participants each (8 SLV213 and 4 placebo), at doses of 400 mg every 12 hours (Q12h), 600 mg Q12h, and 800 mg Q12h administered orally (PO) for 7 days. After each cohort, a Safety Review Committee (SRC) will evaluate the safety of the regimen before proceeding to dose the next cohort.

Randomization will occur into the respective cohorts as above. Upon meeting the Inclusion/Exclusion criteria, subjects will begin treatment with SLV213 or placebo per their assigned cohort. Participants will take their study drug in the fasted state prior to morning and evening meals and will remain as in-patient in the clinical trial unit (CTU) during all treatments and for approximately 48 hours (h) after the last dose for monitoring. After discharge from the CTU, participants will be monitored by CTU staff by telephone to assess for new adverse events (AEs) and use of concomitant medications (ConMeds) since the last visit or contact, approximately

weekly for three weeks. Participants will be asked to return to the CTU for further assessment of moderate or severe AEs. (For further information on study drug administration see [Section 6.1.2](#). List of assessments from Screening to last study visit can be found in the Schedule of Assessments (SOA), [Section 1.2](#), and in [Section 8.1](#) and [Section 8.3](#)).

Objectives

- Primary: To evaluate the safety and tolerability of multiple ascending doses of SLV213 for 7 days in healthy participants.
- Secondary: To characterize the multiple dose PK of SLV213 in healthy participants.

Outcomes / Endpoints

- Primary:
 - Safety: Type, incidence, severity, and relatedness to study drug of all treatment-emergent systemic, laboratory and electrocardiographic (ECG) adverse events (AEs) and serious adverse events (SAEs) in each treatment cohort from the first dose (Day 1) through the last visit (Day 28 ± 2 days).
 - Tolerability: Proportion of participants experiencing any treatment-emergent AEs assessed as related to study drug vs. placebo.

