- Secondary: PK parameter estimates and calculated exposure measures in plasma SLV213 following a single initial dose on Day 1 and after multiple Q12h dose administration for 7 days.

For a full list of Objectives and Outcomes/Endpoints, see [Section 3](#).

Inclusion Criteria

See inclusion criteria in [Section 5.1](#).

Exclusion Criteria

See exclusion criteria in [Section 5.2](#).

Study Phase (if applicable)

Phase 1

Study Population

36 ambulatory healthy participants, age 18-65 years of age inclusive at the time of dosing.

Sites

One clinical site located in the United States.

Study intervention:

- SLV213 capsules containing 100 mg of a defined powder of drug substance K777 hydrochloride. The chemical structure, characteristics and formulation of SLV213 are provided in [Section 6.1.1](#) and [Section 6.2.3](#), and in [Figure 2](#) and [Table 1](#).
- Matching placebo capsules containing 62.5 mg microcrystalline celluloid. The chemical structure, characteristics and formulation are provided in [Section 6.1.1](#) and [Section 6.2.3](#), and in [Figure 3](#) and [Table 2](#)

Each participant will be randomly assigned to receive SLV213 or placebo (SLV213: placebo ratio 2:1) orally (PO) as follows: 4 capsules Q12h in Cohort 1, 6 capsules Q12h in Cohort 2, and 8 capsules Q12h in Cohort 3 daily for 7 days. The SLV213 dose will be 400 mg Q12h, 600 mg Q12h and 800 mg Q12h for participants in Cohorts 1, 2 and 3, respectively, for 7 days.

Study Duration

Screening can occur up to 28 days before the start of dosing. Dosing commences over a period of 7 days at the study site. Participants are followed for 28 (± 2) days after the first dose is administered. The study is expected to complete in 6 months.

Participant Duration

There will be a Screening period of 27 days (Day-28 to Day-2) to determine eligibility and a check-in visit (Day-1) to confirm eligibility for admission. Eligible participants will be monitored as inpatients in the CTU for 9 days, 7 days (Day 1 to Day 7) during active dosing, and for 2 days after dosing (Days 8 and 9) for in-patient follow-up, discharged on Day 9, and followed up to 21 days as out-patients after the last dose, on Days 15 (± 2 days), 21 (± 2 days) and 28 (± 2 days) by phone, and as needed at the CTU for the evaluation of AEs/SAEs. The total participant duration including the screening and post-dosing periods would be up to 56 (± 2 days).

Safety Monitoring

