	
 • $AUC_{(0-\text{last})}$: Area under the plasma concentration - time curve from time zero to the last concentration above the lower limit of quantitation • $AUC_{(0-\tau)}$: Area under the plasma concentration - time curve to the end of the dosing interval • $t_{1/2}$: Terminal half-life • CLT: Total clearance • Ke: terminal phase elimination rate constant • Vd: Volume of distribution • Dose-normalized exposure parameters ($AUC_{(0-\tau)}$/Dose and C_{\max}/Dose) 
The following multiple-dose plasma PK parameters will be computed (if estimable) from the drug total concentration-time data over the 48-hour dosing interval following the evening dose on Day 7 for each cohort.
 
 • $C_{\max,ss}$: observed maximum concentration at steady state • $C_{\min,ss}$: observed minimum concentration at the end of the dosing interval at steady state • C_{avg}: calculated average concentration during the dosing interval • $T_{\max,ss}$: Time of maximum concentration (C_{\max}) at steady state • T_{\min}: Time to minimum concentration (C_{\min}) • $AUC_{(0-48),ss}$: area under the plasma concentration - time curve from 0h (pre-dose) to 48 h after dosing at steady state • $AUC_{(0-\tau),ss}$: Area under the plasma concentration - time curve to the end of the dosing interval at steady state • $t_{1/2}$: Terminal half-life • CLT: Total clearance • Vd,ss: Volume of distribution at steady state • Linearity Index: $AUC_{(0-\tau),ss}$ (Day 7) / $AUC_{(0-\infty)}$ (Day 1) • RAUC: Accumulation ratio for AUC estimated as $AUC_{(0-\tau)}$ (Day 7) / $AUC_{(0-\tau)}$ (Day 1) • RC_{\max}: Accumulation ratio for C_{\max} estimated as C_{\max} (Day 7) / C_{\max} (Day 1). • Dose-normalized exposure parameters ($AUC_{(0-\tau)}$/Dose and C_{\max}/Dose) 
Calculate trough plasma concentrations of total SLV213 at 12h after each morning and evening dose from Day 1 through Day 7.

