4.4 Justification for Dose

Selva has conducted a Phase 1 randomized double-blind placebo-controlled single ascending dose study in healthy volunteers to evaluate the safety, tolerability, and PK of SLV213 following oral administration (Study SLV213-01). Following randomization, five cohorts of 8 participants each (6 active, 2 placebo) received a single dose of the active compound SLV213 or placebo at 50 mg, 100 mg, 200 mg, 400 mg, or 800 mg PO. A SRC evaluated the blinded results of each successive cohort before proceeding to dose the next cohort. Although a clinically significant episode of orthostatic hypotension was observed 30 min after dosing in one participant at the 200 mg dose level, this was not seen in this participant at subsequent time points, nor in any other participant at the 400 mg or 800 mg dose levels. The SRC therefore concluded that no DLT had been seen at any of the dose levels. Pharmacokinetic analyses demonstrated dose dependent C_{max} and AUC. Preliminary modeling of 400 mg and 800 mg BID using predicted blood levels showed exposures comparable to concentrations measured in preclinical efficacy models. It is therefore concluded that 400 mg Q12h, 600 mg Q12h and 800 mg Q12h dosing should be well tolerated. Further description of the results of the SLV213-01 study is provided in the IB.

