8.4 Study Drug Administration

Participants will receive daily dosing Q12h (morning and evening) for 7 days, with the first dose of the study drug administered in the morning on Day 1 and the last dose in the evening of Day 7. The study product will be administered orally with at least 240 mL (8 fluid ounces) or more of tap or bottled water.

All participants are required to fast for the indicated periods before and after dosing as follows:

- Day 1, Morning dose: at least 8h before and 4h after the morning dose
- Day 1, Evening dose: at least 2h before and 1h after the evening dose

- Days 2-6, Both morning and evening doses: at least 2h before and 1h after each dose
- Day 7, Morning dose: at least 2h before and 1h after the morning dose
- Day 7, Evening dose: at least 8h before and 4h after the evening dose

Fluids will be allowed during fasting except for at least 1h before and 1h after each scheduled dose.

The meal schedule will be structured to restrict meals before and after each dose as required. Standard meals will be provided at appropriate times before and after each drug administration and the time the last meal was consumed before and after each dose on Days 1 to 7 will be recorded.

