## CLT

Total clearance (CLT) will be obtained from Dose/AUC∞. If % $AUC_{\text{ex}}$  is  $>20\%$ , the estimated CLT value will be excluded from statistical summaries of parameter estimates and downstream calculations. CLT will be obtained from the  $CL\_F\_obs$  parameter calculated by WinNonlin®. Clearance will be reported in units of L/h.

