**Vd,ss**

$V_{d,ss}$  is the volume of distribution at steady state. It will be obtained from  $Vz\_F\_obs$  in WinNonlin®.

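### In an oral-only study, total clearance and Vd,ss cannot be estimated: the SAP reports CL/F on Day 1, Vz/F in place of Vss, and a Day 7 clearance that is neither CL nor CL/F

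*Protocol*

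**What the plan says.** **Endpoints.** Protocol Section 3 puts "CLT: Total clearance" in both the Day 1 and the Day 7 list, and "Vd,ss: Volume of distribution at steady state" in the Day 7 list. Each is to be computed if estimable. Protocol 9.3.7 and SAP Section 3 repeat them.

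**Route.** Dosing is oral throughout: the top planned level is "800 mg Q12h administered orally (PO) for 7 days" (Protocol Synopsis), and "The study product will be administered orally with at least 240 mL" of water (Protocol 8.4). The earlier human study was also oral (Protocol 4.4). The only intravenous dosing described is in dogs (Protocol 2.3.1). No human F appears in either document.

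**Calculation.** SAP 10.1.1 says total clearance "will be obtained from Dose/AUC" to infinity, from the output `CL_F_obs`. It calculates Vd as CL_T/Ke, from `Vz_F_obs`, calls it apparent and ties it to the terminal phase. SAP 10.1.2 takes Day 7 CL_T from the same `CL_F_obs` and refers back to 10.1.1 for details. Of Vd,ss it says that it "is the volume of distribution at steady state. It will be obtained from" `Vz_F_obs`.

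**Display.** Table 21 prints CL_T for both days, Vd for Day 1 and Vd,ss for Day 7. Listing 10 prints CL_T and Vd; Listing 11 prints CL_T and Vd,ss. None of these labels carries the word apparent or a /F, and no Table 21 footnote explains them.

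**The concern.** Dose/AUC after an oral dose gives clearance divided by the absorbed fraction, not clearance. A volume built on it inherits the same division. Vz and Vss are also different volumes, so calling a Vz/F output the steady-state volume changes the quantity as well as its scale.

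Day 7 adds a separate fault. AUC from Dose 14 to infinity contains the tail of the previous 13 doses, while the numerator is one dose. The quotient falls below CL/F by an amount that depends on half-life. Someone comparing the two days in Table 21 could read this as slower elimination on repeat dosing when it is only arithmetic.

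The SMC is to use the final PK data in recommending a Phase 2 dose (Protocol 10.1.6), the topline report is meant for planning later trials (SAP 6.2), and only the 400 mg level was enrolled.

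**Working it through.** The documents give no F, clearance, volume or half-life, so there is no stated figure to reproduce. The check uses linear oral models with Q12h dosing and 14 doses (both from the protocol). F, half-life, the absorption rate (ka = 2 per h) and the two-compartment constants are assumptions.

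**1. Day 1 clearance.** AUC(0-∞) = F × Dose/CL, so Dose/AUC(0-∞) = CL/F. The ratio to CL is exactly 1/F: 5 at F = 0.2, 2 at 0.5, 1.25 at 0.8 and 1 at 1.0.

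**2. Day 7 clearance as written.** At steady state AUC(0-τ),ss equals the single-dose AUC(0-∞), so Dose/AUC(0-τ),ss = CL/F. The SAP's definition uses AUC(0-∞) after Dose 14, which is larger by a factor R. For one compartment with k = ln 2/half-life and τ = 12 h,

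R = [ka/(1 − e^(−kτ)) − k]/(ka − k),

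which is close to 1/(1 − e^(−kτ)) when absorption is fast. Example at 12 h: k = 0.0578 and e^(−kτ) = 0.5, so R = (4 − 0.0578)/(2 − 0.0578) = 2.03, and the ratio to CL at F = 0.8 is 1/(0.8 × 2.03) = 0.62.

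| Assumed half-life (h) | R | Day 7 value/CL, F = 0.5 | F = 0.8 | F = 1.0 |
|---|---|---|---|---|
| 2 | 1.02 | 1.96 | 1.23 | 0.98 |
| 4 | 1.16 | 1.73 | 1.08 | 0.86 |
| 6 | 1.35 | 1.48 | 0.92 | 0.74 |
| 12 | 2.03 | 0.99 | 0.62 | 0.49 |

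Numerical integration gave the same values, and using AUC(0-τ),ss returned exactly 1/F in every case. The F = 1.0 column is also the apparent Day 7/Day 1 clearance ratio at any constant F. The SAP's Linearity Index, AUC(0-τ),ss over Day 1 AUC(0-∞), would be 1 in all these cases, so Table 21 could show perfect linearity beside an apparent halving of clearance.

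**3. Which values reach the summary.** SAP 10.1.1 drops CL_T from summaries when more than 20% of AUC(0-∞) is extrapolated. With 12 h of Day 1 sampling, the extrapolated share in the same model is ka·e^(−kτ)/(ka − k): 14% at a 4 h half-life, 27% at 6 h and 51% at 12 h. So in the 6 h and 12 h rows, where R is largest, Day 1 CL_T would be dropped. Day 7 CL_T, with 48 h of sampling, would stay: at 12 h the share is [4 × 0.0625/1.942]/2.03 = 6%.

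**4. Vd,ss.** Vz = CL/λ, where λ is the terminal rate. In a two-compartment model Vss = V1(1 + k12/k21).

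- k10, k12, k21 = 0.3, 0.2, 0.15 per h: λ = 0.0788, Vz = 3.81 V1, Vss = 2.33 V1, Vz/Vss = 1.63.
- 0.5, 0.3, 0.1 per h: λ = 0.0595, Vz = 8.41 V1, Vss = 4 V1, Vz/Vss = 2.10.

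At F = 0.5, Vz/F from AUC(0-τ),ss is 3.26 and 4.20 times Vss. If `Vz_F_obs` carries AUC(0-∞) after Dose 14, as the 10.1.1 definition implies, it is 2.39 and 2.94 times. None equals 1/F = 2. At F = 1 the AUC(0-τ),ss ratios are still 1.63 and 2.10.

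**The case against.** The strongest reply is that the plan hides nothing. It names `CL_F_obs` and `Vz_F_obs`, calls the Day 1 volume apparent, states the oral route throughout and limits every parameter to what is estimable. CL/F and Vz/F are the usual quantities from oral data. The endpoints are descriptive, the study stopped after Cohort 1, an abbreviated report is planned, and relabelling changes no Cmax, AUC, trough or accumulation ratio. The Day 7 cross-reference could also be read as general background rather than as a choice of AUC.

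Much of this stands, and it keeps the priority modest. It does not remove the fault. The estimability clause does not help, because the software returns a number that is then printed under a name it does not fit. SAP 10.1.1 itself describes `Vz_F_obs` as a terminal-phase volume, and 10.1.2 gives the same output the steady-state name. The only definition of clearance in the SAP is Dose/AUC(0-∞), and 10.1.2 names the same output.

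A reader might also infer a salt versus free-base error. The Synopsis describes "SLV213 capsules containing 100 mg of a defined powder of drug substance K777 hydrochloride", Protocol 6.2.3 words the content as K777, and Protocol Table 1 gives molecular weights of 611.19 and 574.73, a ratio of 1.063. If salt mass were entered as dose and the assay reported free base, CL/F and Vz/F would be 6.3% high. But neither document says which mass basis is entered or which the assay uses, and Protocol 9.3.7 leaves detailed PK methods to a separate PK Plan. If the bases match, the error is zero. This is a query, not a demonstrated fault.

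**Conclusion.** The point holds as a fault of naming and definition in the secondary PK endpoints. Absolute clearance and Vss cannot be estimated from these data. Three different discrepancies follow:

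- Day 1 CL_T is CL/F, off by 1/F.
- Vd,ss is Vz/F, off by (Vz/Vss)/F, with a further 1/R if Day 7 AUC(0-∞) is used.
- Day 7 CL_T is about CL/(F × R), which is neither CL nor CL/F.

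A reader might infer that every reported value simply exceeds the named endpoint by 1/F. The documents do not support that. It is exact only for Day 1 clearance and vanishes at F = 1. It fails for Vd,ss, because Vz is another volume. It fails for Day 7 clearance even in direction: at an assumed F of 0.8 the ratio to CL runs from 1.23 at a 2 h half-life to 0.62 at 12 h.

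The sizes rest on linear kinetics, steady state at Dose 14 (which SAP 10.1.2 also assumes), and assumed values of F, half-life, absorption rate and two-compartment constants. The actual size cannot be derived from the documents. No hypothesis test or sample size depends on it.

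**What to change.** Issue a SAP addendum before final data lock, which SAP Section 15 allows, and record the departure from Protocol Sections 3 and 9.3.7 there and in the CSR:

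1. Rename CL_T to CL/F and Vd to Vz/F in SAP Sections 3 and 10.1, Table 21 and Listings 10 and 11.
2. Define Day 7 CL/F as Dose/AUC(0-τ),ss with τ = 12 h, and Day 7 Vz/F as that value divided by the Day 7 Ke. State τ explicitly: SAP 10.1.2 calls the 48 h after Dose 14 a dosing interval, while its RAUC definition uses 0 to 12 h.
3. Withdraw Vd,ss as not estimable from oral data and report Vz/F in its place.
4. Optionally, footnote in Table 21 the mass basis of the dose and of the assay result.

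Renaming without step 2 would leave the Day 7 row mislabelled. With step 2, Day 7 CL/F no longer depends on extrapolation to infinity. The cost is wording, one change of AUC and the withdrawal of one listed descriptive endpoint. If lock has passed, SAP Section 15 bars an amendment, and the correction belongs in the CSR as a justified deviation.

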4. STUDY DESIGN

4.1 Overall Design

This Phase 1 double blind, placebo-controlled study will consist of three sequential inpatient cohorts of 12 healthy participants each (8 SLV213 and 4 placebo), at doses of 400 mg Q12h, 600 mg Q12h, and 800 mg Q12h for 7 days administered PO. After each cohort has been dosed, a SRC will evaluate the safety of the regimen to Day 15 before proceeding to dose the next cohort. The study will be carried out in the US at a single clinical trial unit (CTU). Subjects who have consented to participate in the study, as evidenced by signing the informed consent form (ICF), will undergo study procedures to determine their eligibility to receive study drug.

Upon meeting Inclusion/Exclusion criteria, participants will begin dosing with SLV213 or placebo per their allotted cohort. Participants will take their study drug prior to morning and evening meals. AEs will be noted and graded per the protocol Toxicity Grading Tables (See [Appendix A](#)). Visit assessments are shown in the schedule of events ([Section 1.2](#)) and [Section 8.1](#) and [Section 8.3](#).

Participants will be assigned to receive their treatment according to the randomization carried out by the clinical site. For each dosing cohort, randomized participants will be assigned a unique number. Participants will be replaced if they withdraw or are withdrawn prior to Day 1 of treatment. The replacement participant would receive the same treatment that the participant being replaced would have received. A unique number will be the only participant identifier used on all sample collections and return of results. The site's unblinded pharmacist or qualified designee will provide each participant's study drug to blinded clinical staff at the participating site. All doses will be administered to the participant at the site by delegated staff under the supervision of licensed clinical staff authorized to administer study drug (PI, or sub-investigator or licensed clinicians listed on Form FDA 1572). The investigational drug blind is maintained by the dispensing pharmacist through a randomization schedule.

A schematic of the study design is presented in [Section 1.3](#). The schedule of activities is in [Section 1.2](#).

Full details about timing of analyses are found in [Section 9.3.2](#).

Details of the SMC oversight are found in [Section 10.1.6](#).

4.2 Dose Escalation

Participants will be enrolled in MAD cohorts. Dosing to the next cohort will be done sequentially only after the safety assessments to Day 15 have been completed to ensure adequate time for review of all available safety and tolerability data and the safety review committee (SRC) confirms that Halting Criteria have not been met.

4.3 Scientific Rationale for Study Design

Given that the present study constitutes a follow-up to a completed SAD Phase 1 safety trial, a placebo control will also be utilized for the current MAD study. In light of this, healthy volunteers

aged 18 - 65 will be selected in a randomized fashion to constitute a representative sample of the broader population affected by COVID-19. Due to the MAD nature of this trial, the study will allow for an assessment of safety and PK of multiple doses of SLV213 over a period of 7 days.

4.4 Justification for Dose

Selva has conducted a Phase 1 randomized double-blind placebo-controlled single ascending dose study in healthy volunteers to evaluate the safety, tolerability, and PK of SLV213 following oral administration (Study SLV213-01). Following randomization, five cohorts of 8 participants each (6 active, 2 placebo) received a single dose of the active compound SLV213 or placebo at 50 mg, 100 mg, 200 mg, 400 mg, or 800 mg PO. A SRC evaluated the blinded results of each successive cohort before proceeding to dose the next cohort. Although a clinically significant episode of orthostatic hypotension was observed 30 min after dosing in one participant at the 200 mg dose level, this was not seen in this participant at subsequent time points, nor in any other participant at the 400 mg or 800 mg dose levels. The SRC therefore concluded that no DLT had been seen at any of the dose levels. Pharmacokinetic analyses demonstrated dose dependent C_{max} and AUC. Preliminary modeling of 400 mg and 800 mg BID using predicted blood levels showed exposures comparable to concentrations measured in preclinical efficacy models. It is therefore concluded that 400 mg Q12h, 600 mg Q12h and 800 mg Q12h dosing should be well tolerated. Further description of the results of the SLV213-01 study is provided in the IB.

5. STUDY POPULATION

This study will enroll healthy volunteers 18-65 years old. Participants will be enrolled in an equitable way with best practices to balance sex and age applied to the study population. Recruitment of not more than 5/3 or less than 3/5 M/F ratio for each experimental group and not more than 3/1 or less than 1/3 M/F ratio for each placebo group may be obtained. Should a participant replacement be necessary within a cohort, the replacement participant will receive the same treatment, and attempts will be made to be of the same gender as the withdrawn participant. Participant Inclusion and Exclusion Criteria must be confirmed by a study clinician licensed to make medical diagnoses. No exemptions are granted on Participant Inclusion/Exclusion Criteria in DMID-sponsored studies.

